In response to this knowledge gap, we piloted peer mentoring for caregivers of homebound patients with advanced PD, nested within a trial of interdisciplinary home visits (K23NS097615). This intervention included a five-hour educational workshop among 34 mentors. We matched mentors with caregiver mentees for 16 weeks, and interim analyses of mentees completing the program indicate feasibility and acceptability.

We now propose to adapt, improve, and implement a **pe**er mentor **s**upport and caregiver education (**PERSEVERE**) intervention for LBD caregivers. We will conduct focus groups and interviews with pilot mentors, mentees, and current caregivers to generate feedback on the mentoring curriculum and handbook. We will focus on key areas of LBD caregiving mastery, including: fall prevention, detecting and managing infections, neuropsychiatric symptom management (particularly hallucinations, delusions, delirium, anxiety, and depression), and advance directives. Applying the stress process model of caregiver strain¹⁹, enhanced by feedback and behavior change theories^{20–23}, we will revise the mentor training curriculum, conversation guides, and resource handbook to operationalize LBD caregiving mastery for the key areas above. We will recruit and train a cohort of approximately 30 LBD peer mentors using the revised curriculum, developing their capacity to serve as LBD caregiving mastery coaches. We will assess mentors' caregiver mastery using Pearlin and Schooler's scale pre- and post-training¹⁹. Finally, we will match each mentor with an active LBD caregiver for 16 weeks of peer mentoring using our revised conversation guides and handbook to assess the impact of mentoring on caregiver mastery, strain, anxiety, and depression.

We will pursue the objectives above with the following specific aims:

Aim 1: To operationalize caregiving mastery in LBD, focused on fall prevention, infection and neuropsychiatric symptom management, and advance directives.

H1: By conducting focus groups and interviews with former and potential LBD mentors and mentees, we will refine a practical toolkit, including a training curriculum, resource handbook, and conversation guide.

Aim 2: To test the impact of peer mentor training on LBD caregiver mastery.

H₂: Mentors will demonstrate greater caregiver mastery following training, as demonstrated by improved caregiver mastery and LBD knowledge scores compared to baseline.

Aim 3: To assess the impact of peer mentoring on LBD caregiver mentees.

H3: Family caregivers of patients with LBD will demonstrate increased caregiving mastery, LBD knowledge, and improved social support, after 16 weeks of structured peer mentoring.

This work will identify key features of caregiving mastery and support in LBD, refine and validate a caregiver support toolkit, and test the impact of a theory-driven intervention to mitigate adverse caregiver outcomes.

I.b. Background

PD affects nearly one million individuals in the US, with a 77% projected increase in prevalence by 2030²⁴. With increasing age and PD duration, the prevalence of PD Dementia (PDD) approaches 70%^{25,26}. Conversely, 4.2 to 7.5% of *all* individuals with dementia will be diagnosed with DLB²⁷. DLB and PDD differ in chronology but share similar underlying pathology and neuropsychiatric features—particularly, depression, anxiety, delusions, and hallucinations—hence the umbrella classification of LBD²⁸. As LBD progresses, symptoms increase in number and severity, quality of life worsens, and hospitalizations and caregiver strain increase^{3,29,30}.

The leading causes of hospitalization in LBD are falls, urinary incontinence or infection, dehydration, and neuropsychiatric changes, many of which are preventable or treatable at home if recognized and addressed promptly¹². An independent but related risk factor in both hospitalization and institutionalization in LBD is caregiver strain^{4,8,9}. Once hospitalized or institutionalized, people with LBD suffer excessive iatrogenic morbidity and mortality¹². Despite overwhelming evidence linking caregiver strain to both acute healthcare utilization and to adverse caregiver health consequences³², and despite unmet needs for prognostic counseling and education for LBD caregivers, few interventions have targeted caregiver strain in this population^{31–33}.

[figure not shown]
Early studies matched Alzheimer's Disease (AD) caregivers with peer mentors—former informal AD caregivers—to bolster coping skills and social support^{34–36}. Qualitative data showed benefits for caregivers and mentors, though some quantitative results are equivocal due to variable implementation^{34,37}. There is a knowledge gap regarding the content, logistics, and implementation of peer mentorship, and LBD caregivers face different and greater challenges than their AD parallels³⁸. While peer mentorship yields social support, this may be necessary but insufficient as it does not address other contributors to caregiver strain³⁹.

Caregiver strain and comorbidities have been conceptualized in the Stress Process Model such that *background and context, primary stressors, role strain,* and *intrapsychic strains* interact to yield outcomes of *caregiver stress and strain,* including depression, anxiety, and physical and psychological comorbidities³⁹. Proposed mediators of these relationships are social support, coping, and *mastery*—both competence and confidence as a caregiver²¹. Indeed, Mausbach and colleagues have demonstrated that mastery attenuates the relationship between caregiver stress and depressive symptoms^{20,40}.

We have designed a theory-based intervention of targeted education on common causes of hospitalization in LBD patients, combined with social support from trained peer mentors, to enhance caregivers' mastery and LBD knowledge. Social Cognitive Theory (SCT) proposes that behavior change is dynamic, affected by expectations, observational learning, and reciprocal influences from the environment²³. Figure 1 shows how PERSEVERE applies SCT constructs to the revised Stress Process Model to improve caregiving mastery and ultimately, outcomes. PERSEVERE builds on our pilot framework, qualitative analysis of focus group feedback, and existing LBD and dementia caregiving educational materials.

Preliminary data: The study team is currently completing a study of caregiver peer mentoring in caregivers of patients with PD (Rush IRB # 17080209, PI: [name]). During three five-hour sessions, our team trained 34 caregiver peer mentors who were matched with caregivers of 65 homebound PD patients participating in an ongoing home visit trial. Caregivers were matched with a mentor at home visit 2 and consented to weekly mentoring calls between visits 2 and 3 (~16 weeks). This study has demonstrated the feasibility of this type of peer mentoring program: among 48 caregivers receiving mentoring, 35 have completed the program to date. Those completing the program had a median of 13 mentoring calls (IQR 7.5) with 98% of caregivers finding visits useful, 99% getting along with their mentor, and a wide range of topics covered, from resources to coping strategies. The NIH K23 trial is ongoing. We will analyze change from baseline in caregiver strain, self-efficacy, anxiety, and depression upon study completion. We will also analyze secondary outcomes including changes within mentors themselves.

Figure 1. Conceptual Model of PERSEVERE Interaction and Social Cognitive Theory Constructs with Stress Process Model

mastery and outcome

I.c. Study Design

Reinforcements

Overview: The aims of this study are to 1) operationalize caregiving mastery in LBD, focused in fall prevention, infection and neuropsychiatric symptom management, and advanced directives; 2) test the impact of peer mentor training on LBD caregiver mastery; and 3) assess the impact of peer mentoring on LBD caregiver mentees. We will address these goals by **Aim 1**: convening focus groups with stakeholders to obtain feedback on the existing mentoring curriculum and to reflect on key areas of LBD caregiving mastery for incorporation in the revised curriculum. We will then revise the PERSEVERE curriculum and handbook based on feedback and incorporation of LBD-specific and dementia-relevant educational materials for both social support and LBD mastery education. Aim 2: To test the impact of the peer mentor training on LBD caregiver mastery, we will assess participating mentors' caregiver mastery and LBD knowledge before and after participation in an 6-7 hour mentor training session. Aim 3: The trained mentors will be matched with family caregivers of patients with LBD and complete a 16-week, structured peer mentoring program. We will compare change in caregiver mastery and LBD knowledge between baseline and 16 weeks of social support and education through mentoring calls.

Caregivers will reflect on how they successfully managed problematic patient behaviors/sudden changes, or mentor

will point out and celebrate successes, prompt caregiver on how to reinforce for future

II. Characteristics of the Research Population

experiences of others

likelihood of repetition

Responses to behavior that affect the

II.a. Number of Subjects

Total Number of Subjects: 896 total participants in four different categories: 30 focus group participants (across multiple focus groups, depending on scheduling needs), 800 participants in the online recruitment survey, 36 peer mentors, and 30 caregiver mentees

Focus group participants: 30 participants who will each participate in one focus group of up to 10 participants

Peer mentors: 36 non-professional current or former caregivers (allowing for the dropout of up to 6 mentors)

Caregiver mentees: 30 current non-professional caregivers

Online Recruitment Survey Participants: 800 current caregivers

Power Calculation: This is a pilot study, intended to generate data regarding effect sizes and to inform sample size calculations for a larger, multi-centered randomized controlled trial in the future. Thus, our sample size of 30 mentees is based on historical recruitment to the preceding K23 and anticipated projections for recruitment within the time frame of this one-year grant. Working backwards from 30 mentees requiring a matched mentor and accounting for up to 15% dropout of mentors after training, we will enroll 36 mentors.

II.b. Gender of Subjects

There will be no exclusion of subjects based on gender.

II.c. Age of Subjects

Subjects will be 21-90 years old.

II.d. Racial and Ethnic Origin

There will be no exclusion of subjects based on racial or ethnic characteristics. Study demographics are expected to match those of the population from which it was drawn. However, subjects must be fluent in English to participate in the study due to the general lack of appropriately translated study assessments and to ensure clear communication between mentors and mentees participating in the mentor program.

II.e. Inclusion Criteria

1. Focus group participants

- a. Each subject must be 21 years of age or older. A subject may identify as any sex, any race, and any ethnicity.
- b. Subjects must be either:
 - i. Individuals who served as peer mentors in our previous study of caregiver peer mentoring and completed at least 16 weeks of mentoring.
 - ii. Individuals who were caregiver mentees in our previous study of caregiver peer mentoring who completed 16 weeks of mentoring.
 - iii. Current informal family caregivers of community-dwelling LBD patients in the Chicago area, recruited from Rush University System for Health and Advocate Aurora Health, who have *not* participated in mentoring.
- c. Each subject must be primarily English-speaking.
- d. Each subject must be willing and able to attend a virtual, online focus group via an internet- and video-camera-equipped computer, tablet, or smartphone.

2. Peer mentors

a. Each subject must be 21 years of age or older. A subject may identify as any sex, any race, and any ethnicity.

- b. Each subject must be a non-professional caregiver (defined as *cohabitating with or spending* ≥10 *hours weekly on unpaid caregiving duties*) of LBD patients. Mentors may participate regardless of their loved one's status (living at home, institutionalized, or deceased).
 - If mentors also receive compensation for a portion of their time spent on caregiving duties through state or community programs, they may participate as long as they cohabitate or spend >10 hours providing unpaid care to their loved one.
- c. Each subject must have:
 - >2 years of LBD caregiving experience, or

• >2 years of PD caregiving experience for an individual without cognitive impairment and professional or volunteer experience interacting with individuals with cognitive impairment or dementia, or their caregivers (e.g., support group leader, healthcare professional, counselor, social worker), or

- >4 years of PD caregiving experience for an individual without cognitive impairment
- d. Each subject must be primarily English-speaking.
- e. Each subject must have a working email address and internet access.
- f. Each subject must have a working telephone number at which he or she can be reached and which he or she is willing to share with the matched mentee.
- g. Each subject who will attend an online peer mentor training session must have an internet- and video-camera-equipped computer, tablet, or smartphone.

3. Caregiver mentees

- a. Each subject must be 21 years of age or older. A subject may identify as any sex, any race, and any ethnicity.
- b. Each subject must be a non-professional, unpaid caregiver, as defined above in II.e.2.b., of a community-dwelling LBD patient.
- c. Each subject must be interested in improving their caregiving mastery.
- d. Each subject must be primarily English-speaking.
- e. Each subject must have a working email address and internet access.
- f. Each subject must have a working telephone number at which he or she can be reached and which he or she is willing to share with the matched mentor.

II.f. Exclusion Criteria for all Subjects

- 1. Subjects exhibiting symptoms of a severe psychiatric disorder interfering with their ability to participate in the study, as determined by a study team member or the PI.
- 2. Subjects who are primarily non-English-speaking.
- 3. Terminal illness (life expectancy of < 12 months).

II.g. Vulnerable Subjects

This study will not include children, prisoners, and homeless persons. Participants are not expected to have cognitive impairment, however as it is anticipated that many subjects may be elderly and at risk of age-related cognitive changes as well as neurodegenerative disease, all subjects will be assessed for capacity to consent (see Section V.b.). The consent form will state that participation in our study will *not* affect their loved one's clinical care.

II.h. Online Recruitment Survey Participants

These participants will include individuals who elect to complete an online survey in order to indicate their interest and eligibility to participate in a caregiver peer mentor program.

III. Methods and Procedures

III.a. Aim 1: Subject Identification, Recruitment, Consenting and Study Procedures

Subjects participating in focus groups and interviews will be recruited from 3 different populations: 1) individuals who were caregiver mentees in our previous peer mentoring study, 2) individuals who served as peer mentors and completed 16 weeks of mentoring in our previous peer mentoring study, and 3) individuals who are current informal family caregivers of community-dwelling LBD patients in the Chicago area, recruited from Rush University and Advocate Aurora Health, who have *not* participated in mentoring. A study team member will provide potential participants with information about the research study by reading from an IRB-approved recruitment script. Once they understand study requirements and the schedule of events, have expressed interest in participating and been screened for eligibility, their focus group or interview will be scheduled.

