Once Aim 2 (above) is complete and 36 mentors have been trained, caregiver mentees will be matched with mentors by relationship to LBD patient, then by sex and age, as much as possible. Mentor and mentee preferences expressed in the mentoring preferences survey will be honored to the extent that the study team is able given the available mentor and mentee participants. The study team will contact mentees once a match is available for them. First, the study team will direct the mentee to complete baseline primary and secondary outcome assessments online via REDCap, including: mastery scale¹⁹, LBD knowledge test, loneliness scale⁴¹, Short Zarit Burden Interview (ZBI-12)⁴², Hospital Anxiety and Depression Scale (HADS)⁴³, Geriatric Depression Scale – Short Form (GDS-SF)⁴⁴, and Dementia Attitudes Scale (DAS)⁴⁵ in order to obtain their pre-intervention baseline. The study team will then provide the mentee with contact information for their mentor, and caregivers will be mailed the PERSEVERE handbook.

Mentor-mentee pairs will then begin the 16-week peer mentor program. During this time, pairs will be expected to speak for ≥15-30 minutes weekly, and to review that week's PERSEVERE topics in the handbook before or during each call to facilitate meaningful conversations. Discussions are not scripted and will not necessarily be limited to that week's topics, at the discretion of the participants. Mentors and mentees will complete online study diaries every 2 weeks, assessing intervention fidelity. Up to 3 email reminders will be sent and/or up to 3 phone calls attempted to complete each study diary. Diary entries will include information such as call frequency, duration, topics discussed, and concerns. At the Week 8 or Week 10 survey, all mentees and those mentors who are still actively caregiving for a loved one with LBD will complete the Parkinson's Disease Carer Questionnaire (PDQ-Carer), a novel measure of PD-specific caregiver quality of life. Mentors will participate in 4 recorded monthly conference calls to share successes, challenges, and feedback, and to ask questions of and be supported by the study team.

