- IV. Aim 3 (caregiver peer mentoring): We will analyze data fidelity by summarizing categorical variables by frequencies and percentages and will assess continuous variables for normality, summarized by mean/standard deviation or median/interquartile range. We will describe the baseline demographics, patient characteristics (including fall frequency and acute healthcare utilization), mastery, LBD knowledge, loneliness, ZBI, HADS, GDS-SF, and DAS of caregivers. Bivariate analyses will compare change between baseline and 16 weeks of mentoring in each of the above, using paired t-test or Wilcoxon sign rank, as appropriate. We will also compare change in PDQ-Carer between mid-study and Week 16 as an exploratory outcome. To examine potential covariate effects, we will run a series of repeated measures ANCOVAs for pre- and post- primary and secondary outcome measures using demographic and confounder variables as nuisance variables. These analyses will be considered exploratory due to the loss of degrees of freedom resulting from the covariates. Mentor program fidelity metrics including *dropout* rate and reasons, time spent on phone calls, number of phone calls, and topics discussed will be calculated

based on responses obtained from biweekly online study diary entries. Qualitative data will be gathered from the monthly mentor conference calls via notes taken by the study team; framework analysis will be applied to identify key themes regarding successes, challenges, and recommendations for improving the program.

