Caregiver peer mentors: The potential direct benefits to caregiver peer mentors include validation of their lived experiences and accumulated knowledge as caregivers to a loved one with LBD, providing some potential degree of closure or purpose. Caregiver peer mentors may have previously been involved with other caregivers but become disconnected if/when their loved one with LBD passed away, and by attending the mentor training session, establishing a mentoring relationship, and participating in conference calls, may rejoin the caregiver community and derive benefits from social interactions and shared experiences.

Caregiver mentees: The potential direct benefits to mentees include increased mastery due to the relationship and discussions held with their mentor, decreased depression, anxiety, and caregiver strain due to the positive relationship with emotional support from a caregiver peer mentor.

All subjects: All subjects' involvement will contribute to scientific knowledge determining whether a formal, 16week mentoring program can have an impact on caregiver mastery, strain, anxiety, and depression. This study and future studies may provide a model of care to improve quality of life and caregiver strain for hundreds of thousands of individuals with LBD and related disorders.

V. Subject Consent

V.a. Process of Consent

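### The pilot is said to yield effect sizes and show the impact of mentoring, but single-arm before-after change cannot do this, and the estimates it can give are not planned

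*Combined protocol and SAP*

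**What the plan says.** **Purpose.** II.a (Power Calculation) says the study is a pilot "intended to generate data regarding effect sizes and to inform sample size calculations for a larger, multi-centered randomized controlled trial in the future". The 30 mentees come from recruitment experience and the grant's time frame. No effect size, SD, power or precision target is given.

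**Claims about mentoring.** The opening objectives plan 16 weeks of mentoring "to assess the impact of mentoring on caregiver mastery, strain, anxiety, and depression". The closing sentence of the aims says the work will "test the impact of a theory-driven intervention to mitigate adverse caregiver outcomes". The overview in I.c says the study will "assess the impact of peer mentoring on LBD caregiver mentees". IV.b tells all subjects that they contribute to "determining whether a formal, 16week mentoring program can have an impact on caregiver mastery, strain, anxiety, and depression". Aim 2 uses the same impact wording for mentor training, in the aims and in I.c.

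**Design and analysis.** In III.c, once a match is available, "the study team will direct the mentee to complete baseline primary and secondary outcome assessments online via REDCap". Every mentee is then mentored, and no concurrent, waitlist or historical comparator is described. Under III.e item IV, "Bivariate analyses will compare change between baseline and 16 weeks of mentoring in each of the above", by paired t-test or Wilcoxon test. Item III treats mentors the same way, before and after training.

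**Cautions already present.** Item IV calls the covariate-adjusted models exploratory because covariates use up degrees of freedom, and it calls the PDQ-Carer comparison exploratory. Neither label covers the unadjusted tests of mastery, knowledge and loneliness, and neither concerns the absence of a control group.

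**The concern.** A paired comparison in one group estimates how much mentees changed over 16 weeks. It does not estimate how much more they changed than they would have without a mentor, which is what an impact claim or a randomised trial's target difference refers to.

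The documents suggest non-mentoring change in both directions. I.b says caregiver strain rises as the disease advances, which could hide a benefit. Eligibility requires mentees to want better caregiving mastery, and the LBD knowledge test is given twice, so scores could also rise without any mentor effect. The covariate models adjust within the same mentored group and cannot supply the missing contrast. In Aim 2 the first comparison falls within one training day, so retesting is the main issue there. The comparison extending to the end of mentoring is exposed to time trend as well.

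Two things are at stake: how this study's results are described, and whether it leaves a later trial with usable planning inputs.

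**Working it through.** **1. The plan's own figures.** Mentors: 30 / (1 − 0.15) = 35.3, rounded up to 36, which reproduces the stated number. The 30 mentees are not derived from a formula, so there is nothing to reproduce.

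**2. What the paired test responds to.** Suppose mentoring has no effect, but mentees improve for other reasons by an assumed amount, in units of the SD of change. With 30 complete pairs and a two-sided 5% paired t-test, the noncentrality is that amount × √30. The chance of a significant improvement is about 18% for 0.2, 36% for 0.3 and 56% for 0.4. A significant result therefore does not by itself show impact.

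**3. If the raw change were used to size a trial (illustration).** Assumptions: two arms, two-sided 5%, 80% power at the observed change, and a share *f* of that change not due to mentoring. The documents give no value for *f*.

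- Planned noncentrality: 1.96 + 0.8416 = 2.8016.
- True power ≈ Φ(2.8016 × (1 − f) − 1.96).
- Required size relative to planned: 1 / (1 − f)².

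| f | True power | Required / planned size |
|---|---|---|
| 10% | Φ(0.561) = 71% | 1.23 |
| 25% | Φ(0.141) = 56% | 1.78 |
| 50% | Φ(−0.559) = 29% | 4.0 |
| −25% (worsening hides benefit) | Φ(1.542) = 94% | 0.64, so 1 / 0.64 = 1.56 times larger than needed |

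I give ratios and no absolute sizes, because those depend on which SD standardises the effect. With equal SDs at both times, an effect in baseline-SD units is √(2(1 − r)) times the effect in SD-of-change units. That factor is 1.0 at r = 0.5 and 0.77 at r = 0.7. Without the pre-post correlation r, the conversion cannot be made.

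**4. What item IV secures.** It commits to tests, and to mean/SD or median/IQR according to normality. That sentence opens by referring to data fidelity, so it is not clearly the rule for outcomes. On either reading, no mean change, confidence interval or pre-post correlation is planned for any outcome.

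**5. Precision at n = 30.**

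- SD: √(29/χ²) at the 97.5% and 2.5% points gives 0.80 to 1.34 times the estimate.
- Correlation of 0.7 (assumed): Fisher z = 0.867 ± 1.96/√27, so 0.45 to 0.85.
- Retention of 24/30 (assumed): Wilson interval 63% to 90%.
- Observed change of 0.5 SD of change (assumed): noncentral-t interval 0.12 to 0.88, before any question of bias.

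**The case against.** The strongest reply is that this is an openly labelled pilot that leaves the controlled question to a randomised trial. The Aim 3 hypothesis is worded as improvement after 16 weeks, and both I.c and III.e speak of comparing change, so the impact wording is largely editorial. That reply stands as to the design. A single-arm pilot sized on recruitment is a sound choice, and no control arm is being asked for. It does not remove the mismatch, because the pilot sentence itself names effect sizes for a randomised trial as the purpose.

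Three stronger readings are tempting, and the documents do not support them:

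- **That the raw change will be the later trial's target difference.** No section says so; II.a says only that the pilot will inform sample size calculations. Misuse in a later trial is hypothetical.
- **That the pilot fails to collect planning inputs.** Dropout and reasons, call frequency and duration, missed calls and topic coverage are planned in the outcomes figure and item IV of III.e. Item V adds quarterly review of accrual and adherence. The gap is narrower: change estimates, SDs reported whatever the distribution, correlations and intervals. All can be computed later from the stored paired data.
- **That the later trial would be too small.** The documents' explicit statement on drift concerns rising strain, which points towards hidden benefit and an oversized trial. No drift is given for mastery, knowledge or loneliness. The power figures would be the same for any one-arm pilot and do not measure this one's bias.

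**Conclusion.** The concern holds in limited form. Followed as written, the plan would describe uncontrolled within-person change as impact and as an effect size, for mentees in Aim 3 and likewise for mentors in Aim 2. It would also report tests without the estimates that a single arm can validly give. This is a mismatch between conclusion and design, and a gap in reporting. It is not a flaw in the choice of a one-arm pilot or in its size.

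The facts about design and wording rest on the text available for review, which contains no statement limiting the interpretation. The size of any consequence rests on an assumed share of non-mentoring change: about 56% true power at 25% and 29% at 50%, with an oversized trial if worsening hides benefit. The change is worth making because it is cheap and affects what the study may claim.

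**What to change.** 1. **III.e item IV.** For each outcome measured at baseline and week 16, report the mean change with its 95% CI, the SD at both times and of the change, and the pre-post correlation, whatever the normality result. Add median/IQR where the distribution is skewed. PDQ-Carer has no baseline measurement and falls outside this line.
2. **II.a, Power Calculation.** Say that the pilot informs the outcome SD, pre-post correlation, recruitment, retention and adherence, each with a confidence interval. Say also that the uncontrolled pre-post change is not an estimate of the between-arm effect.
3. **Opening objectives and aims, I.c and IV.b.** For Aim 3 and likewise Aim 2, state that results will be interpreted as within-person change and not as the causal impact of mentoring or training.

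**Cost.** An amendment to wording and one reporting line, with no added participants, assessments or hypothesis tests. The stated conclusion becomes more modest, change without mentoring stays unmeasured, and the planning inputs stay imprecise at n = 30, which is why their intervals should be shown.
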